3.1. Sample Size

The sample size calculation was conducted in G*power (version 3.1.9.4, University of Kiel, Kiel, German) using a Poisson regression model. The calculation was made with certain assumptions (80% power, 5% significance level, 50% difference in fall rate (favouring the PBT), and 20% dropout rate) and an expected average fall rate of 0.85.[18–21] This resulted in an estimated required sample size of 70 participants in each group.

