3.2. Randomisation and Blinding

After the pre-training tests, participants will be randomly allocated to either the PBT or treadmill walking group using a permuted block randomisation module in REDCap to ensure similar group sizes (Research Electronic Data Capture; version 9.5.6). Random block sizes (two, four, six, or eight) will ensure that allocation concealment is maintained. The allocation sequence will be generated by a research staff member not involved in enrolling or assigning participants to groups.

4. Study Population

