Short Falls Efficacy Scale	7-item questionnaire; score from 7-28 (lower score indicates better performance)	Pre-training test; post-training test; 26- week follow-up; 52-week follow-up	Continuous (ordinal)	Normal distribution of residuals and random effects * [◊] Homogeneity of variance [◊]	Linear mixed-effects model [○]

EuroQoL 5D-5L	
5-item questionnaire and visual analogue scale; index from 0-1 (higher score indicates better performance)
 
Visual analogue scale from 0-100 (higher score indicates better performance)
	
Pre-training test; post-training test; 26-week follow-up; 52-week follow-up
	
Continuous (ordinal)
	
Normal distribution of residuals and random effects^{*†} Homogeneity of variance[‡]
	
Linear mixed-effects model[○]

---------------	---	--	-----------------------------	---	---

* Examined by visual inspection of histograms and QQ-plots; [†] Examined by visually inspecting residuals plotted against fitted values; [‡] If data is not normal-distributed; [‡] Violations of assumptions will be noted; however, no alternative method will be used, as the linear mixed-effects model is robust against such violations; [○] Participant ID as the random effect

Sensitivity analysis

Fall outcomes

For the primary outcome (fall rates) and secondary fall outcomes, a sensitivity analysis adjusting for known confounders (age, sex, and previous falls) will be conducted to evaluate the robustness of the results. Furthermore, if the count variable data is over-dispersed, a poisons regression with bootstrapping will be performed; however, a sensitivity analysis without bootstrapping will also be carried out. These analyses were planned before the commencement of data collection. Additional fall rate sensitivity analyses 1) only including participants with no prior history of falls 12 months before study commencement and 2) only including participants with a history of falls 12 months before study commencement will also be conducted. These sensitivity analyses were planned after data collection began.

Fall-related risk factor outcomes

Before data collection commenced, it was determined to conduct a sensitivity analysis on the secondary fall-related risk factors adjusting for age, sex, and previous falls will be carried out.

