6.3. Major Protocol Deviations

Major protocol deviations will be reported in the trial registration at ClinicalTrials.gov ([NCT04733222](https://clinicaltrials.gov/ct2/show/NCT04733222)), the local ethics committee, and the SAP.

7. Implementation of Analysis Plan

The data will be exported from REDCap to the statistical program STATA. An external statistician not involved in the study will assist with the statistical test.

STATA CODE

Poisson regression (example of code for fall rate):
poisson fallrate ib1.group, irr exposure(personyear)

Poisson regression with bootstrapping (example of code for fall rate):
poisson fallrate ib1.group, irr exposure(personyear) vce(bootstrap, reps(1000))

Poisson regression adjusting for age, sex, and fall history (example of code for fall rate):
poisson fallrate ib1.group age i.sex i.prev_faller, irr exposure(personyear)

Poisson regression with robust error variance (example of code for proportion of fallers):
glm faller ib1.group, fam(poisson) link(log) vce(robust) eform

Poisson regression with robust error variance adjusting for age, sex, and fall history (example of code for proportion of fallers):
glm faller ib1.group age i.sex i.prev_faller, fam(poisson) link(log) vce(robust) eform

Cox survival analysis (example of code for time to first fall):
stset firstfall, failure(faller==1)
stcox group

Cox survival analysis adjusted for age, sex, and fall history (example of code for time to first fall):

```
stset firstfall, failure(faller==1)  
stcox group age i.sex i.prev_faller
```

unpaired t-test (example of code for Global Patient Impression of Change (gpic)):

```
ttest gpic, by(group) unpaired
```

Unpaired two-sample Wilcoxon test (example of code for Global Patient Impression of Change):

```
ranksum gpic, by(group)
```

Fisher's exact (example of code for the proportion of fallers following slip perturbation at pre-training (t1)):

```
tabulate lab_slip_t1 group, exact
```

Linear mixed-effects model (example of code for single-task gait speed):

```
mixed gaitspeed_st group time || record_id:, var reml
```

In case of significant interaction effect, a posthoc analysis adjusted using the Bonferroni method is employed using the following code:

```
contrast rb1.time#group, mcompare(bonferroni)
```

Linear mixed-effects model adjusting for age, sex, and fall history (example of code for single-task gait speed):

```
mixed gaitspeed_st age i.sex i.prev_faller group##time || record_id:, var reml
```

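### Making the pre-planned age, sex and previous-falls model primary for fall rate and proportion of fallers would be a modest, nearly free efficiency gain over the unadjusted model

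*Combined protocol and SAP*

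**What the plan says.** Table 1 assigns Poisson regression to the primary outcome, fall rate. The example command under STATA CODE has group as its only predictor and person-years as exposure, and section 5.1 confirms that follow-up time enters as an offset. If mean and variance differ, the Table 1 footnote and the Sensitivity analysis section switch to bootstrapped standard errors.

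Under Sensitivity analysis, Fall outcomes, the plan states that "a sensitivity analysis adjusting for known confounders (age, sex, and previous falls) will be conducted" for the primary and secondary fall outcomes, and that this was decided before data collection began. The command is "poisson fallrate ib1.group age i.sex i.prev_faller, irr exposure(personyear" followed by the closing bracket, with no variance option. The corresponding adjusted command for proportion of fallers does request robust errors.

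Section 2.3 lists sex and fall history among the data collected, and age is needed for eligibility (section 4.1). Section 3.2 allocates participants "using a permuted block randomisation module in REDCap to ensure similar group sizes" and states no stratification factor.

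**The concern.** The plan treats fall history as important: it names it among the covariates to adjust for, and it adds fall-rate analyses split by history of falls. The primary estimate nevertheless makes no use of it. Two things are at stake.

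- **Precision.** Differences between people that fall history could explain stay in the residual variation. When the standard error reflects that variation, the confidence interval is wider than it need be.
- **Chance imbalance.** Without stratification, one arm may by chance contain more previous fallers, and the unadjusted rate ratio moves with that.

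The sample size leaves little slack to absorb either. For the fall rate and the proportion of fallers, a log-link ratio keeps its meaning under adjustment if the treatment effect is common across covariate levels, so these gains would not change what is estimated.

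**Working it through.** **Inputs from section 3.1:** "80% power, 5% significance level", taken as two-sided; "50% difference in fall rate (favouring the PBT"), so IRR = 0.5; "an expected average fall rate of 0.85", read as the control-arm rate λ per person-year; "20% dropout rate". Exposure is taken as one year.

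**1. The plan's own figure.** The Wald formula for Poisson regression with 1:1 allocation is

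N = (z_α + z_β)² × (2 + 2/IRR) / (λ × (ln IRR)²)

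= (1.960 + 0.842)² × 6 / (0.85 × 0.4805) = 115.3, so 116 in total or 58 per arm. Multiplying by 1.2 gives 69.6, so 70 per arm, the stated figure. (Dividing by 0.8 would give 73.) The calculation has no covariate and no overdispersion term.

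**2. Power left after dropout.** Losing 20% of 70 leaves n = 56 per arm. The variance of the log rate ratio is

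v = 1/(nλ) + 1/(nλ × IRR) + 2C/n

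where C is the squared coefficient of variation of the underlying rates between people. With C = 0, v = 1/47.6 + 1/23.8 = 0.0630. Then 0.693/√0.0630 − 1.960 = 0.80, and power is 0.788.

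**3. Gain from adjustment, by formula.** Let k be the residual frailty variance and c the part of the squared coefficient of variation that the covariates explain. Unadjusted, C = (1 + k)(1 + c) − 1; adjusted, C = k. With 35% previous fallers (assumed), a previous-faller rate ratio of 1.5, 2 or 3 implies c = 0.041, 0.125 or 0.315. The table takes c from 0.05 to 0.30.

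| k | Unadjusted power (c = 0.05 to 0.30) | Adjusted power |
|---|---|---|
| 0 | 0.777 to 0.723 | 0.788 |
| 0.5 | 0.669 to 0.605 | 0.683 |
| 1.0 | 0.582 to 0.516 | 0.597 |

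The gain is 1 to 8 points. The formula treats the covariate effects as known, so simulation is the better guide.

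**4. Gain from adjustment, by simulation.** 3,000 trials per cell, 56 per arm, IRR 0.5, 35% previous fallers, and assumed rate ratios of 1.2 per SD of age and 1.1 for sex. Robust errors stand in for the bootstrap. Entries are power, unadjusted to adjusted.

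| Frailty variance | Rate ratio 1.5 | Rate ratio 2 | Rate ratio 3 |
|---|---|---|---|
| 0 | 0.790 to 0.798 | 0.778 to 0.797 | 0.719 to 0.781 |
| 0.5 | 0.674 to 0.687 | 0.668 to 0.686 | 0.604 to 0.663 |
| 1.0 | 0.587 to 0.586 | 0.573 to 0.581 | 0.527 to 0.564 |

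The gain is about 0 to 1 point at a rate ratio of 1.5, 1 to 2 at 2, and 4 to 6 at 3. The Monte Carlo standard error of one entry is about √(0.6 × 0.4/3000) = 0.9 points, so the smallest differences are not distinguishable from none.

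**5. The same comparison with model-based Poisson errors.** There is no power gain: 0.807 against 0.796 and 0.776 against 0.774 at frailty 0; 0.745 against 0.753 at frailty 0.5 and rate ratio 3. These errors are too small under overdispersion. Type I error was 0.054 to 0.206 unadjusted and 0.047 to 0.178 adjusted.

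**6. Chance imbalance.** With 35% previous fallers, the SD of the difference in proportions between arms is √(2 × 0.35 × 0.65/56) = 0.090. An imbalance of 1.96 SD is 0.177, for example 43.8% against 26.2%. The unadjusted IRR is then multiplied by (1 + 0.438)/(1 + 0.262) = 1.14 at a rate ratio of 2, or (1 + 2 × 0.438)/(1 + 2 × 0.262) = 1.23 at 3. A true 0.50 would read 0.57 or 0.62; with the imbalance reversed, 0.44 or 0.41.

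**The case against.** The strongest reply is that nothing here is wrong. With no stratification factor stated, no design variable is missing from the model, and the unadjusted comparison matches the basis of the sample size. Chance imbalance is ordinary sampling variation, which a correctly estimated interval covers; it is not bias. The adjusted result will be reported anyway. All of this stands. A reader might infer that the primary analysis is invalid or biased, and the documents do not support that.

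A reader might also infer that power is lost whatever standard error is used. It is not: under the default model-based error the gain is nil. The gain depends on the bootstrap route. That route is likely to be taken, because the footnote invokes it whenever mean and variance differ, and a strong effect of previous falls itself pushes the variance above the mean.

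A third tempting reading is that every secondary fall outcome should be adjusted. That fails. The Cox hazard ratio changes meaning under adjustment; Fisher's exact, t and Wilcoxon tests take no covariates; and fractures may be too few. If 2% to 5% of 112 completers had one (an assumption), that is about 2 to 6 events for a model with four predictors.

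Finally, the change is more than exchanging two labels. The adjusted fall-rate command lacks a variance option, and the hierarchy of analyses would have to be formally amended.

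**Conclusion.** The point holds as an efficiency improvement for fall rate and proportion of fallers. For fall rate with bootstrap or robust errors, the gain is about 0 to 6 points of power at 56 completers per arm. Its upper end needs previous fallers to fall at about three times the rate of others. The proportion of previous fallers, the strength of the covariates and the frailty variance are all assumptions. The power gain for proportion of fallers was not calculated; the case there rests on the same covariates and on a risk ratio that keeps its meaning.

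The protection against chance imbalance in fall history does not depend on the choice of standard error. Nor should adjustment be read as a rescue for power. At a rate ratio of 1.5, moving frailty variance from 0 to 1 takes unadjusted power from 0.790 to 0.587, and adjustment recovers very little of that.

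**What to change.** Before the groups are compared:

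1. Make the model with age, sex and previous falls the primary analysis of fall rate, and add `vce(bootstrap, reps(1000))` or `vce(robust)` to the adjusted command.
2. Do the same for proportion of fallers; its adjusted command already has robust errors.
3. Report the unadjusted models for both outcomes as sensitivity analyses.
4. Leave the Cox, Fisher, t-test/Wilcoxon and sparse fracture analyses as planned.

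The cost is a dated SAP amendment recording that the hierarchy changed before any comparison of the groups, plus a minor code edit. No new data are needed and the sample size stays at 70 per group. Because the adjusted model was itself planned before data collection, promoting it at that stage would not be a data-driven choice.

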6.3. Major Protocol Deviations

Major protocol deviations will be reported in the trial registration at ClinicalTrials.gov ([NCT04733222](https://clinicaltrials.gov/ct2/show/NCT04733222)), the local ethics committee, and the SAP.

7. Implementation of Analysis Plan

The data will be exported from REDCap to the statistical program STATA. An external statistician not involved in the study will assist with the statistical test.

STATA CODE

Poisson regression (example of code for fall rate):
poisson fallrate ib1.group, irr exposure(personyear)

Poisson regression with bootstrapping (example of code for fall rate):
poisson fallrate ib1.group, irr exposure(personyear) vce(bootstrap, reps(1000))

Poisson regression adjusting for age, sex, and fall history (example of code for fall rate):
poisson fallrate ib1.group age i.sex i.prev_faller, irr exposure(personyear)

Poisson regression with robust error variance (example of code for proportion of fallers):
glm faller ib1.group, fam(poisson) link(log) vce(robust) eform

Poisson regression with robust error variance adjusting for age, sex, and fall history (example of code for proportion of fallers):
glm faller ib1.group age i.sex i.prev_faller, fam(poisson) link(log) vce(robust) eform

Cox survival analysis (example of code for time to first fall):
stset firstfall, failure(faller==1)
stcox group

Cox survival analysis adjusted for age, sex, and fall history (example of code for time to first fall):

```
stset firstfall, failure(faller==1)  
stcox group age i.sex i.prev_faller
```

unpaired t-test (example of code for Global Patient Impression of Change (gpic)):

```
ttest gpic, by(group) unpaired
```

Unpaired two-sample Wilcoxon test (example of code for Global Patient Impression of Change):

```
ranksum gpic, by(group)
```

Fisher's exact (example of code for the proportion of fallers following slip perturbation at pre-training (t1)):

```
tabulate lab_slip_t1 group, exact
```

Linear mixed-effects model (example of code for single-task gait speed):

```
mixed gaitspeed_st group time || record_id:, var reml
```

In case of significant interaction effect, a posthoc analysis adjusted using the Bonferroni method is employed using the following code:

```
contrast rb1.time#group, mcompare(bonferroni)
```

Linear mixed-effects model adjusting for age, sex, and fall history (example of code for single-task gait speed):

```
mixed gaitspeed_st age i.sex i.prev_faller group##time || record_id:, var reml
```

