2.2. Secondary Objectives and Outcomes

The secondary objectives are to evaluate the effects on additional fall metrics and the potential transfer effects of PBT to other relevant physical, cognitive, and social-psychological risk factors.

The secondary fall metrics include the proportion of fallers, the time to first fall, the proportion with at least one fall-related fracture, the rate of fall-related fractures, the proportion with at least one fall-related injury, the rate of fall-related injury, the proportion with at least one fall-related health-care contact, and the rate of fall-related health-care contact. It is expected that the proportion of fallers is 50% lower in the PBT-group compared to the treadmill walking group.[6,9] However, we do not have enough evidence regarding the remaining fall-related outcomes to make hypothesis hereof; thus, these outcomes are considered exploratory.

The secondary fall-related risk factors included are single- and dual-task gait speed, reaction time, single- and dual-task static balance, lower extremity performance, executive function, health-related quality of life, and fear of falling. These secondary outcomes were chosen as they all have been identified as fall risk markers [10–16]. However, there is insufficient information about such outcomes following PBT; therefore, we consider these outcomes exploratory.

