2.4.2. Secondary Endpoints

Secondary outcomes and their endpoints are outlined in table 1 and 2. The secondary fall outcomes will be collected using the fall calendars for 12 months. The fall-related risk factor outcomes will be collected at the pre- and post-training test and the 26- and 52-week follow-up.

3. Study Design

This study is designed as an assessor-blinded, randomised, parallel-group (1:1 ratio), controlled trial

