5.1 Missing data

The number of missing observations and the associated reasons will be reported. For the primary outcome, fall rates, missing data will not be imputed; however, the analysis will be adjusted for follow-up time (days of follow-up will be used as an offset). Likewise, missing data regarding the secondary binary outcomes will neither be imputed, but the modified Poisson regression will be adjusted for person-years (days of follow-up will be used as an offset). For participants who do not return any fall calendars 0 falls and 0 person-years will be registered. However, if more than 10% of data is missing in any outcomes, a sensitivity analysis utilising multiple imputations will be conducted.

Missing data in continuous outcome are expected to be missing at random; thus, they will not be imputed as it has shown that multiple imputations do not add any benefits to a linear mixed-effects model.[25]

6. Statistical Analysis

All statistical tests will be performed using an intention-to-treat approach. Moreover, a per-protocol analysis will also be performed, including only participants who complete 75% or more of the training sessions. The secondary outcome will not be adjusted for multiple comparisons; thus, these results should be considered exploratory.

Count data will be reported as incidence rate ratios (IRR) with 95% confidence intervals (95% CI). Binary outcomes will be reported as risk ratios (RR) and 95% CIs. When appropriate, continuous variables will be reported as either mean and standard deviation or median and interquartile range.

Table 1 Variables, measures, and methods of analysis for fall outcomes.

Primary outcome					
Variable/outcome	Mode of assessing	Time frame	Variable type	Assumption	Methods of analysis
Fall rate (falls per person-year)	Fall calendars	Continuously for 12 months	Count	Equal mean and variance *	Poisson regression Alternative: Bootstrapping [†]
Secondary fall outcomes					
Variable/outcome	Mode of assessing	Time frame	Variable type	Assumption	Methods of analysis
Proportion of fallers	Fall calendars	Continuously for 12 months	Binary	Equal mean and variance *	Poisson regression with robust error variance
Time to first fall	Fall calendars	Continuously for 12 months	Survival	Linear relationship between log hazard and covariate ^a	Cox proportional hazard

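### The group-by-visit mixed model for the Table 2 outcomes has only a participant random intercept; if within-person correlation decays, post-training intervals are too wide and 52-week intervals too narrow

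*Combined protocol and SAP*

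**What the plan says.** Section 7 (STATA CODE) gives two mixed-model lines for the risk-factor outcomes, with gait speed as the example. The unadjusted line is "mixed gaitspeed_st group time || record_id:, var reml". The line adjusted for age, sex and fall history is "mixed gaitspeed_st age i.sex i.prev_faller group##time || record_id:, var reml". Neither has a random slope, a residual covariance structure or a robust variance. The Table 2 footnote agrees: "Participant ID as the random effect".

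After a significant interaction, the unadjusted analysis goes on to "contrast rb1.time#group, mcompare(bonferroni"); the adjusted analysis uses the same contrast without Bonferroni. This contrast compares the groups on change from the reference visit.

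Section 2.4.2 says the outcomes are "collected at the pre- and post-training test and the 26- and 52-week follow-up". Table 2 lists normality and homogeneity of variance as assumptions, checked visually. No check of within-person correlation is listed. On missing values, section 5.1 states: "Missing data in continuous outcome are expected to be missing at random". It therefore plans no imputation and relies on the mixed model. On the status of these outcomes, section 2.2 says: "therefore, we consider these outcomes exploratory".

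**The concern.** A random intercept with independent, equal-variance residuals is compound symmetry: every visit has the same variance and every pair of visits the same correlation. The four visits are unequally spaced. Two tests on either side of a short training course would usually correlate more strongly than two tests a year apart. The model nevertheless uses one pooled residual variance for every change-from-baseline contrast, and its model-based standard errors do not correct themselves if that is wrong.

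Transfer to gait, balance, reaction time, cognition and fear of falling is a stated secondary objective, and the same model serves every Table 2 outcome. If correlation decays, an immediate training effect is tested with too little power, and a 52-week effect is judged against an interval that is too short. The mixed model is also the only missing-data method for these outcomes, and under missing at random it depends on a sound covariance model.

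**Working it through.** **Inputs from the documents.** Four visits; 1:1 allocation; 70 per group; 20% dropout, so 70 × 0.8 = 56 per arm. The SAP states no SD, correlation or power for the risk-factor outcomes, so it has no figure to reproduce here. Its sample size concerns the fall rate only.

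**Assumptions.** Equal variances (σ²), complete data, and separate group-by-visit means. Three correlation patterns with the pre-training visit are used (pre-post/pre-26/pre-52). In each, the post-26 and post-52 correlations equal the pre-26 and pre-52 values, and the 26-52 correlation is 0.75.

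**Formula.** Let r_k be the correlation between baseline and visit k, and r̄ the mean of the six pairwise correlations. For the between-group difference in change from baseline to visit k:

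- true variance = 2σ²(1 − r_k) × 2/n
- variance reported by the random-intercept model = 2σ²(1 − r̄) × 2/n
- model SE / true SE = √[(1 − r̄)/(1 − r_k)]

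**Interval widths.**

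| Pattern | r̄ | Post-training ratio | 52-week ratio |
|---|---|---|---|
| Gentle 0.80/0.75/0.70 | 4.45/6 = 0.742 | √(0.258/0.20) = 1.14 | √(0.258/0.30) = 0.93 |
| Middle 0.85/0.75/0.65 | 4.40/6 = 0.733 | √(0.267/0.15) = 1.33 | √(0.267/0.35) = 0.87 |
| Steep 0.90/0.75/0.60 | 4.35/6 = 0.725 | √(0.275/0.10) = 1.66 | √(0.275/0.40) = 0.83 |

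The post-training interval is therefore 14%, 33% or 66% too wide, and the 52-week interval 7%, 13% or 17% too narrow.

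**The planned sequence.** The contrasts are reached only through the interaction test, so the whole sequence was simulated: a 3-df interaction test at 5%, then Bonferroni over three contrasts, with 56 per arm, complete data and at least 8,000 trials per scenario. The post-training effect was sized for 80% power in a single unadjusted test with the correct SE. The 52-week column is under no effect.

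| Pattern | Post-training power: unstructured → random intercept | 52-week false positives: unstructured → random intercept |
|---|---|---|
| Gentle | about 64% → 51% | about 1.4% → 2% |
| Middle | about 63% → 32% | about 1.4% → 3% |
| Steep | about 62% → 10% | about 1.4% → 4% |

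**Other patterns.**

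- All correlations equal: ratio 1.00 and 95% coverage at every visit.
- Baseline correlated 0.6 with each later visit, later visits 0.8 with each other: r̄ = (3 × 0.6 + 3 × 0.8)/6 = 0.70. The ratio is √(0.30/0.40) = 0.87 at every follow-up visit (coverage 91%), so all intervals are too narrow.
- Post-training visit the odd one out (0.60 with the others, which correlate 0.75): r̄ = 0.675. The ratio is √(0.325/0.40) = 0.90 post-training and √(0.325/0.25) = 1.14 at 52 weeks, the reverse direction.

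**The case against.** Five points can be made on the other side.

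1. **The unadjusted line produces no visit-specific interval.** This stands. As printed, it has no interaction and estimates one overall group effect. An overall group effect from a random-intercept model had 94.6% to 94.9% coverage under every correlation pattern tried with complete data. The point therefore attaches to the interaction line and the contrast step. The SAP does place the Bonferroni contrast directly after the unadjusted line, so visit contrasts are intended there too. That the line cannot supply them is a separate inconsistency.
2. **The gate and Bonferroni step protect the 52-week test.** This largely stands. A reader might take the ungated 1.96 test, which gives 6.9%, 8.7% and 10.4% false positives in the three patterns, as the trial's error rate. The planned sequence gives about 2% to 4%. With the gate but no Bonferroni, as in the adjusted analysis, it gives about 3% to 6%. The gate does not restore the lost post-training power.
3. **The direction is assumed.** This stands. A reader might infer that early intervals will be too wide and late ones too narrow for every Table 2 outcome. The documents give no correlations, visit SDs or pre-to-post gap, and other patterns behave differently.
4. **The footnote does not forbid a different covariance.** This stands. The statement "Violations of assumptions will be noted; however, no alternative method will be used, as the linear mixed-effects model is robust against such violations" belongs to the listed assumptions of normality and homogeneity of variance. It should not be read as ruling out a change of covariance structure. It offers no remedy for a wrong one either.
5. **The outcomes are exploratory.** This stands and limits the weight of the point.

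**Conclusion.** The point holds conditionally. The SAP imposes equal variance and equal correlation on four unequally spaced visits, and plans neither a check of that correlation nor a robust variance. If correlation falls with time and variances are similar, the main cost is lost power for the immediate transfer effect: about 13 percentage points under gentle decay (64% to 51%) and roughly half the power under middle decay. The rise in 52-week false positives is smaller, and the gated, Bonferroni-adjusted rate stays below 5%, although the nominal interval is still too short.

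These sizes rest on assumed correlations, equal variances and complete data; the effect of dropout is not quantified here. If the correlations are in fact equal, nothing is lost. The primary fall-rate analysis is not touched. This is a worthwhile, inexpensive improvement to an exploratory analysis, not a threat to the trial's main conclusion.

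**What to change.** In both the unadjusted and adjusted models, fit visit as a factor with its group interaction and an unstructured within-person covariance, for example:

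`mixed gaitspeed_st i.group##i.time || record_id:, noconstant residuals(unstructured, t(time)) reml dfmethod(kroger)`

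Add age, sex and fall history for the adjusted version. Pre-specify a fallback if the model does not converge: a random intercept plus exponential serial correlation in weeks. State the covariance structure and the fallback in the Table 2 footnote.

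The cost is two lines of SAP code, ten covariance parameters instead of two (estimable with about 140 participants), and a small risk of non-convergence, which the fallback covers. If compound symmetry is true, little is lost. The same edit puts the interaction into the unadjusted model, so that its planned contrast can be run.
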